### **7.4. Vital Signs**

Summary statistics for pulse, blood pressure, body temperature, and weight will be presented at baseline and each visit. Vital signs values and changes from baseline to each visit will be summarized using descriptive statistics.

The incidence of potentially clinically significant abnormal values will be summarized for vital signs using descriptive statistics with the criteria specified in [Table 1](#). These summaries will include all postbaseline values (including scheduled, unscheduled, and withdrawal visits). Note that in order to qualify as potentially clinically significant abnormal, a value needs to meet both criteria below: ie, have a value beyond the criterion value and a change of at least the magnitude specified in the change relative to baseline column.

**Table 1: Criteria for Potentially Clinically Significant Vital Signs**

Vital Sign	Criterion value	Change relative to baseline
Pulse	$\geq 120$ bpm	Increase of $\geq 15$
	$\leq 50$ bpm	Decrease of $\geq 15$
Systolic blood pressure	$\geq 180$ mm Hg	Increase of $\geq 20$
	$\leq 90$ mm Hg	Decrease of $\geq 20$
Diastolic blood pressure	$\geq 105$ mm Hg	Increase of $\geq 15$
	$\leq 50$ mm Hg	Decrease of $\geq 15$
Body temperature	$\geq 38.3^{\circ}\text{C}$	Change of $\geq 1.1^{\circ}\text{C}$

### 7.5. Electrocardiography

Shifts (normal and abnormal) from baseline to overall finding and each visit will be summarized using patient counts. For overall finding, the summary will use the worst postbaseline finding for the patient (the abnormal finding if there are both normal and abnormal findings). Summary statistics for ECG variables will be presented at baseline and each visit. Actual values and changes from baseline to each visit will be summarized using descriptive statistics.

The incidence of potentially clinically significant abnormal values for ECG variables will be summarized using descriptive statistics with the criterion specified below.

- QTcF values  $>450$  ms or  $>480$  ms or  $>500$  ms.
- QTcF change from baseline values  $>30$  or  $>60$ .
- PR change from baseline  $\geq 25\%$  and value  $>200$ .
- QRS change from baseline  $\geq 25\%$  and value  $>110$ .
- Heart rate value  $<60$  bpm or  $>100$  bpm.

### 7.6. Physical Examinations

Shifts (normal and abnormal) from baseline to each visit for each category will be summarized using patient counts.

### 7.7. Concomitant Medications or Therapies

Concomitant medications and therapies, including medications that are taken on an as needed basis and occasional therapies, will be monitored during the study. All concomitant medications will be coded using the WHO drug.

The incidence of concomitant medications and therapies will be summarized using descriptive statistics by therapeutic class category and PT. Patients are counted only once in each therapeutic class, and only once in each PT category. Concomitant medications and therapies will include all

medications taken and therapies administered from the first day of study drug administration up to the end of study as defined in the study protocol.

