#### **4.6.7 End of Study/Early Termination Visit**

Patients who complete all scheduled visits (remote video and TC) will have procedures and assessments performed via remote video conference and mobile nurse visit at the EOS/ET visit. Patients who withdraw from the study before completing the treatment period will have the EOS visit (or ET) procedures and assessments performed at his/her final visit.

The end of study is defined as the last visit of the last patient.

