#### **4.6.9 Withdrawal From Treatment**

If the patient wishes to stop treatment, is judged by the investigator (or qualified designee) to not be suitable for continued therapy, or the study is discontinued, a remote visit ("withdrawal visit", ET visit) should be performed and the patient withdrawn from the study. A (telephone) follow-up visit (30 d TC follow up) to collect and report AEs, concomitant medications (as well as inquiry about changes in use of benzodiazepines and antidepressants), changes in use of alcohol and drugs associated with substance abuse (legal or illicit), C-SSRS, and an abbreviated PBA-s assessment should take place 1 month after the actual discontinuation of IMP took place.

Additional criteria for discontinuation of IMP for individual patients are detailed in Section [7.7.1](#).

Patients who discontinue IMP due to safety or tolerability reasons may continue in the study off IMP and perform the scheduled visits and assessments.

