### **5.7.4 Medication That May Cause QTc Prolongation**

In addition to the currently disallowed concomitant medications in the protocol, patients on pridopidine should not be allowed to take the following medications known to have a

---

substantial increase on QT interval: antidepressants (citalopram and escitalopram); antipsychotics (haloperidol, pimozide, clozapine, sertindole, and ziprasidone); and lithium. If these drugs are required for management of the patient, pridopidine should be discontinued.

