## **11 ADMINISTRATIVE PROCEDURES**

The study will be carried out in accordance with the study protocol, ICH-GCP guidelines, appropriate FDA-CFRs, and local regulatory requirements.

CROs and/or independent contract personnel may be contracted, subject to approval by Teva, to manage and monitor the study, to provide services for data management and statistical analysis, to provide regulatory advice and services, to handle the reporting of SAEs, to provide services for laboratory analysis, to package and distribute the clinical study supplies, and to provide advice on ICH-GCP and quality, and to audit the investigational centers/contractors involved in the conduct of the study.

A full statistical analysis plan will be written in conjunction with the protocol and finalized before database lock. A statistical report will be produced and a final integrated clinical and statistical report will be written in accordance with ICH-GCP by an appropriately qualified individual.

For the purposes of notification to regulatory authorities and ethics committees the end of the study will be defined as being the date of the last visit of the last patient undergoing the study.

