#### **Withdrawal from treatment**

If the patient wishes to stop the drug, or is judged by the investigator to not be suitable for continued therapy, or the study is discontinued, a clinic visit ("withdrawal visit", end of study drug visit) should be performed and the patient withdrawn from the study. A (telephone) follow-up visit (30 d TC F/U) to collect and report AEs (as well as inquiry about changes in use of benzodiazepines and antidepressants, and inquiry about changes in use of alcohol and illicit drugs), C-SSRS and an abbreviated PBA-s assessment should take place one month after the actual discontinuation of study drug took place.

Patients who discontinue study medication due to safety or tolerability reasons may continue in the study off drug and perform the scheduled visits and assessments.

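### SAP 7.7 sets no cut at the patient's last dose, so the concomitant-medication table cannot separate drugs taken with pridopidine from drugs first started after it was stopped

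*SAP*

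**What the plan says.** SAP 7.7 gives the incidence of concomitant medications by therapeutic class and preferred term, counting each patient once per class and once per term. The window covers "medications taken and therapies administered from the first day of study drug administration up to the end of study as defined in the study protocol".

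The protocol defines that end point for the study, not for the patient. Section 4.6.7 has "The end of study is defined as the last visit of the last patient", and section 11, for notifying authorities and ethics committees, says that "the end of the study will be defined as being the date of the last visit of the last patient undergoing the study".

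Two provisions create observed time off drug:

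- SAP 2.1, under Withdrawal from treatment: "Patients who discontinue study medication due to safety or tolerability reasons may continue in the study off drug and perform the scheduled visits and assessments". The scheduled visits described in SAP 2.1 include a review of concomitant medication.
- The same SAP text has a telephone follow-up that "should take place one month after the actual discontinuation of study drug took place", with questions about changes in benzodiazepines and antidepressants. Protocol 4.6.9 describes this call as one "to collect and report AEs, concomitant medications" and other items.

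Protocol 5.7.4 names antidepressants, antipsychotics and lithium that are not to be taken with pridopidine because of their effect on the QT interval, and adds: "If these drugs are required for management of the patient, pridopidine should be discontinued". Under Protocol 5.7.5, a patient who starts a disallowed medication listed in the Operations Manual has to come off study drug.

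**The concern.** SAP 2.3 lists concomitant medication use among the safety measures, and long-term safety is part of the primary objective. A reader goes to this table to see which drugs were taken alongside pridopidine, and whether disallowed drugs were among them.

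Under the SAP 7.7 window, a drug first started after a patient's last dose counts in the same way as one taken during treatment. The mixing need not be random: where sections 5.7.4 and 5.7.5 apply, stopping pridopidine and starting certain drugs are linked by rule. A patient who stopped and then began a listed drug would fall in the same cell as a patient who took both together. The table has no timing with which to separate them.

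**Working it through.** The plan gives no figure on this point to reproduce. The check compares definitions, followed by one illustration of scale.

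**1. Windows side by side**

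| Source | Window |
|---|---|
| SAP 7.7, medications | first dose day to the protocol's end of study |
| SAP 7.2, exposure | first to last day of study drug |
| SAP 7.3, adverse events | on or after the first dose day, no upper limit |
| Protocol 8.9.2, adverse events | until 2 weeks after the last dose, for events starting in Open-HART or Open-PRIDE-HD |
| Protocol 7.1.3, treatment-emergent events | from start of study drug through the time of residual drug effect |

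The medication table and the exposure table therefore cover different periods. SAP 7.7 has no start-date rule, no residual-effect window and no on-drug/off-drug split, and no other SAP section supplies one.

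**2. Are off-drug medications recorded?** Yes, by two routes: scheduled visits for patients who continue off drug, and the one-month call. A drug first started after the last dose and recorded by either route meets the SAP 7.7 definition.

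**3. Where does the window end in practice?** The protocol's end of study is the last patient's last visit, but a patient's records end at that patient's own last contact. The excess over time on drug is therefore any off-drug follow-up, or about one month where there is only the call.

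**4. Scale.** Let T be years on treatment (assumed, since the documents give no distribution) and take 30 days for the follow-up. The off-drug share of the window is 30 / (T × 365.25 + 30).

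- T = 0.5: 30 / (182.625 + 30) = 30 / 212.625 = 14.1%
- T = 1: 30 / (365.25 + 30) = 30 / 395.25 = 7.6%
- T = 6: 30 / (2191.5 + 30) = 30 / 2221.5 = 1.4%

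For a patient who stays off drug for F days, F replaces 30. The SAP sets no limit on F. These are shares of observation time and indicate opportunity only. SAP 7.7 counts patients, so none of them is the error in a reported cell.

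**The case against.** The case for leaving SAP 7.7 alone has several parts.

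- **Withdrawal is the default.** SAP 2.1 and Protocol 7.7.2 have a patient who stops treatment withdrawn from the study. Continuing off drug is an option for those who stop for safety or tolerability. Protocol 5.7.1 and 5.7.3 withdraw patients who start the drugs they cover, so for those drugs little more than the one-month call remains. Needing a QT-prolonging drug is not plainly a safety or tolerability stop either. This stands, and it limits the size.
- **The window is openly stated.** Protocol 8.7 speaks of concomitant medication during the study and plans a listing. If that listing shows dates, a reader could separate cases by hand. Protocol violations are summarised separately under SAP 5.8. This also stands, but it does not repair the summary table.
- **The window matches adverse events.** SAP 7.3 has no upper limit, so dropping later medications would leave late events without the matching medications. This is a reason to tabulate later medications separately and not to remove them.
- **Document versions differ.** SAP 2.1 says that it follows Amendment 04 and that Amendment 05 was not implemented. The protocol text supplied is Amendment 05, so the Amendment 04 wording on end of study and on QT-prolonging drugs cannot be checked. The SAP's own withdrawal text still establishes the off-drug time.

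Two stronger readings are tempting. A reader might infer that the table reports co-use of prohibited drugs that never happened. The documents do not support that: they do not show that any such case occurred, and SAP 7.7 states a time window without claiming simultaneous use. A reader might also infer that every patient's window runs on to the last patient's last visit. Step 3 of the working shows that this date adds no data after the patient's own last contact.

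**Conclusion.** The point holds as a minor correction. SAP 7.7 pools medications taken during treatment with medications first started after it, and its table cannot separate them. The drugs for which this matters most are those that Protocol 5.7.4 and 5.7.5 link to stopping pridopidine.

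The number of patients affected is unknown. Where the only off-drug observation is the 30-day follow-up, the extra time is small for long-treated patients and more noticeable for early stoppers. It can grow for anyone who remains off drug.

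The conclusion rests on SAP 7.7 being applied as written and on medications being recorded after the last dose, as the visit descriptions provide. It concerns what one descriptive safety table can show. No efficacy, adverse-event or ECG figure depends on it.

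**What to change.** In SAP 7.7, define concomitant medications and therapies as those taken on any day from the first to the last dose of study drug, including those already ongoing at first dose. Tabulate those first started after the last dose in a separate post-treatment summary, so that nothing is dropped. This uses the same end points as exposure in SAP 7.2.

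If a residual-effect window after the last dose is wanted, state its length in SAP 7.7 and apply the same window to adverse events in SAP 7.3, which at present sets none.

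The cost is a sentence or so in SAP 7.7 and one extra table. No new data collection is needed. Adding a residual-effect window would cost more, because it also requires a decision on SAP 7.3. The basic split does not depend on that decision.

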### **7.8. Other Safety Assessments**

Summary statistics for the C-SSRS baseline version will be presented at screening. Patients with suicidal ideation and behavior items will be summarized as categorical data using descriptive statistics.

Summary statistics for the C-SSRS last visit version will be presented at overall postbaseline. Patients with suicidal ideation and behavior items will be summarized as categorical data using descriptive statistics.

## **8. STATISTICAL SOFTWARE**

All data listings, summaries, and statistical analyses will be generated using SAS® version 9.4 or later.

**9. CHANGES TO ANALYSES SPECIFIED IN THE STUDY  
PROTOCOL**

There are no changes to analyses specified in the study protocol.
